4 STUDY DESIGN

4.1 OVERALL DESIGN

The study is a randomized control trial (RCT) involving two groups – IBMT (Arm 1: experimental manipulation) and health education (HE) (Arm 2: control group) group. Participants in each group will be assessed at baseline, post-intervention, and at 3-month follow-up using behavioral, cognitive, and brain assessments as described in Section 1.3. Automatic randomization will be conducted by study staff and used to assign participants to each arm/group condition using an algorithm before the baseline assessment. This randomization procedure ensures balance between groups on gender while also balancing total treatment numbers.

4.2 SCIENTIFIC RATIONALE FOR STUDY DESIGN

To evaluate the effects of our experimental manipulation, we need an active control group for this RCT study design. The HE has been used as a control condition in many previous published studies and is an accepted control intervention. Thus, we use it as a control condition in our study design. There are no known or potential problems associated with the control group.

4.3 JUSTIFICATION FOR INTERVENTION

The chosen 10-sessions of experimental manipulation - IBMT has been shown to improve behavior, cognition, and brain in previous RCTs in healthy adults. Thus, we choose to use the same setup and design, and expect the same length and frequency of the intervention would be appropriate for older adults.

4.4 END-OF-STUDY DEFINITION

A participant is considered to have completed the study if he or she has completed the baseline assessment, 10 intervention sessions, post-assessment, and 3-month follow-up assessment.

5 STUDY POPULATION

5.1 INCLUSION CRITERIA

In order to be eligible to participate in this study, an individual must meet all of the following criteria:

1. Provision of signed and dated informed consent form
2. Males and females; Age 40-65 years old.
3. Able to read/understand English
4. Normal performance using standardized cognitive tests
5. Self-reported decline in cognitive capacity such as memory loss
6. Eligible for non-invasive fMRI
7. Willing to be randomized
8. Free of any severe psychiatric diagnoses or medication that may affect participation

5.2 EXCLUSION CRITERIA

An individual who meets any of the following criteria will be excluded from participation in this study:

1. Medical disorders or medications that affect the central and autonomic nervous system; or a positive pregnancy test result (females)
2. Unable to provide consent or understand study procedures due to mental illness or cognitive limitations
3. Previous meditation experiences
4. Evidence of illicit drug use
5. Metal or metallic materials in the body such as pacemaker

5.3 LIFESTYLE CONSIDERATIONS

N/A

5.4 SCREEN FAILURES

Screen failures are defined as participants who consent to participate in this study but are not subsequently assigned to the study intervention or entered in the study. Individuals who do not meet the criteria for participation in this trial (screen failure) because of meeting one or more exclusion criteria that are likely to change over time may be rescreened. Examples include the successful removal of metal devices that previously made them ineligible for an MRI scan. Rescreened participants will be assigned the same participant number as for the initial screening.

5.5 STRATEGIES FOR RECRUITMENT AND RETENTION

We anticipate to enroll 40 participants (males and females) ages from 40 to 65 years old across different race and ethnicity based on local demographic characteristics. Subjects will be recruited through print and media ads within local community. This will include radio and online ads and recruitment through social media. Flyers will be distributed throughout the local community. Based on our and other's previous experiences in longitudinal studies, about 5-10% of participants will dropout over the study period due to illness or relocation. We plan a dropout rate of 10% for this brief intervention. We propose to recruit 40 older adults of which 36 (90%) will complete the study.

Compensation and Retention. Participants will be financially compensated with \$300 in total for completing the study protocol (approximately for 15 hours of time); participants who only partially complete the protocol will be compensated based on prorated hours. To maximize participant retention we will maintain contact with participants over time via frequent assessment intervals (e.g., requiring a functioning phone number and email address to contact participants by phone or email as needed, and obtaining the name, address, and phone number of at least 2 friends or classmates who can provide contact information for the participants, should we be unable to contact them during the study; emails and reminder phone calls prior to all study visits; offer flexible scheduling options for assessment (including weekends); provide fair compensation to participants; and maintain positive relations with participants. These procedures were used to maintain adequate participant retention in our prior NIH studies.

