6.1.2 ADMINISTRATION AND/OR DOSING

Both arms of interventions will be administered as a group by trained interventionists. Both interventions will have 10 consecutive group sessions, and the completion of all 10 sessions is considered to be having a “full-dose” intervention. Participants in the same arm/group will interact with a shared interventionist.

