9.3 POPULATIONS FOR ANALYSES

The analysis population will be Modified Intention-to-Treat Analysis Population. Specifically, these participants are those who completed the full-dose of the intervention (10 sessions) and have complete and usable data for the primary endpoints.

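### Section 9.2 bases power on 40 after attrition, but Section 5.5 leaves 36 of 40, and the Section 9.3 analysis set has no allowance for missed sessions or unusable data

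*Combined protocol and SAP*

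**What the plan says.** Three numbers or sets describe who is left at the end, and they differ.

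- **Section 5.5 (recruitment and retention).** Enrolment is 40: "We anticipate to enroll 40 participants (males and females) ages from 40 to 65 years old". Past experience is that "about 5-10% of participants will dropout over the study period due to illness or relocation". The plan then says "We plan a dropout rate of 10% for this brief intervention" and concludes "We propose to recruit 40 older adults of which 36 (90%) will complete the study".
- **Section 4.4 (end of study).** A completer is someone who "has completed the baseline assessment, 10 intervention sessions, post-assessment, and 3-month follow-up assessment".
- **Section 9.3 (analysis population).** The set is called modified intention-to-treat but consists of "those who completed the full-dose of the intervention (10 sessions) and have complete and usable data for the primary endpoints". Section 6.1.2 fixes the meaning of full dose: "the completion of all 10 sessions is considered to be having a “full-dose” intervention".
- **Section 9.4.2.** Missing data on the primary endpoints lead to case-wise deletion.
- **Section 9.2.** The target of 40 is described as the number after attrition, and 80% power at alpha 0.05 is claimed for 40 subjects at f = 0.3.

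Section 6.4 says attendance will be tracked. No section gives an expected attendance rate or a rate of unusable data.

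**The concern.** The power statement should describe the sample that will be analysed. Here it describes a sample that the recruitment section says will not exist: 40 is the number enrolled in 5.5 and the number surviving attrition in 9.2.

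The 36 in 5.5 is not shown to be the analysed number either. It comes from a dropout rate supported by experience of illness and relocation. Under 9.3, a participant who stays to the end but misses one of ten sessions is also removed, as is one who attends everything but has an unusable primary measurement. Neither route has a stated allowance.

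There is a second consequence. Excluding people for incomplete attendance conditions the comparison on something that happens after randomisation. Participants with usable outcome data would be discarded, and if attendance differs between the two programmes, the arms compared would no longer be those that randomisation formed.

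**Working it through.** **1. Reproduce the figure in 5.5.** 40 × (1 − 0.10) = 36, which is 90%. The multiplication is correct.

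**2. Compare with 9.2.** To have 40 after 10% attrition, enrolment would have to be 40 / 0.90 = 44.4, so 45. The plan enrols 40. The two sections cannot both hold.

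**3. Compare with 9.3.** For the analysed number to equal 36 at 10% dropout, every remaining participant must attend all 10 sessions and have complete, usable primary data. If the loss to illness or relocation is 5%, 40 × 0.95 = 38 remain, and 36 is still reached with further loss of up to 1 − 36/38 = 5.3%, that is, two people.

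**4. Range below 36 (assumed rates, not from the documents).**
- Further loss among the 36 of 0%, 5%, 10%, 20%: 36 × (1 − loss) = 36, 34.2, 32.4, 28.8.
- If each session were attended independently with probability p, all ten are attended with probability p^10. For p = 0.99, 0.98, 0.95 this is 0.904, 0.817, 0.599, and 36 becomes 32.6, 29.4, 21.6. Independence is a pessimistic choice; if absences cluster in the same people, the loss is smaller.

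**5. Power at the smaller N.** Test: group × time interaction, 2 groups, m = 3 visits, alpha 0.05, sphericity assumed. Inputs from 9.2: f = 0.3 and correlation ρ = 0.30 to 0.60 for behavioural measures. Default G*Power form, without covariates: λ = N·m·f²/(1 − ρ), with df 2 and 2(N − 2). Example at ρ = 0.30: λ = 40 × 3 × 0.09 / 0.70 = 15.4 at N = 40, and 36 × 3 × 0.09 / 0.70 = 13.9 at N = 36.

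| N | Power at f = 0.3, ρ = 0.30 to 0.60 | f detectable with 80% power, ρ = 0.30 / 0.60 |
|---|---|---|
| 40 | 94.1% to 99.7% | 0.242 / 0.183 |
| 36 | 91.4% to 99.4% | 0.256 / 0.193 |
| 32 | 87.6% to 98.7% | 0.272 / 0.205 |
| 28 | 82.3% to 97.3% | 0.292 / 0.221 |
| 26 | 79.0% to 96.2% | 0.303 / 0.229 |

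Adding the age and sex covariates to the error df hardly changes this: 91–99% at 36, 84–98% at 29, 71–92% at 22.

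**6. The result depends on the convention.** In the same form with ρ = 0, power is 83.0% at N = 40 and 78.5% at N = 36. If the 80% claim is taken literally and the effect is set to give exactly 80% at N = 40, power is about 75% at 36, 65% at 29 and 51% at 22. Section 9.2 does not say which convention or which correlation lies behind its 80%.

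**The case against.** The strongest case against the point is this. The arithmetic in 5.5 is right. The sentence that plans 10% names no cause, and completing the study is a term that 4.4 defines, so 36 can be read as an all-in estimate of 4.4 completers, set at the top of a 5–10% range. Section 5.5 never calls 36 the analysis set, and the demand for usable data is in 9.3, not in 4.4. Some losses may be recovered: 7.3 has staff try to reschedule a missed visit within a week, and 7.2 allows replacement of participants who are randomised but receive no intervention. On the plan's own f = 0.3 in the default form, power stays above 80% until N is about 26.

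Most of this stands, and it limits the point. A reader might infer that 36 is a miscalculation, or that the plan's rules are bound to deliver fewer than 36, perhaps 22 to 33. The documents support neither. With no attendance or missing-data rate, the shortfall may be nil, and 22 to 33 is only what follows from assuming 95–99% independent attendance. A reader might also infer that power drops to 50–75%. That follows only for an effect chosen to have 80% power at 40, not from the stated f and correlations in the default form.

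The objection does not remove the conflict between 40 after attrition in 9.2 and 36 in 5.5, or supply an allowance for the 9.3 exclusions. Rescheduling is written for visits in general, and whether a group session can be made up is not stated. Replacement does not reach someone who starts and then misses a session.

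**Conclusion.** The point holds in a limited form. From stated figures alone, 9.2 and 5.5 are inconsistent: 40 after attrition against 36. At the planned 10% dropout, 36 is an upper limit for the analysed N. This assumes that the 10% is not offset by replacing participants lost before their first session, which 5.5 does not address. How far below 36 the 9.3 set would fall cannot be derived.

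The cost of using 36 instead of 40 is small. The f detectable with 80% power rises from 0.242 to 0.256 at ρ = 0.30, and power falls by about 3 percentage points at f = 0.3, or about 5 if the effect has exactly 80% power at 40. Larger losses rest on assumed attendance. The case for changing 9.3 does not depend on those figures: the all-10-sessions condition is a post-randomisation exclusion that discards participants who have data.

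**What to change.** 1. **Section 9.2.** Replace 40 after attrition with at most 36. Restate the power or detectable effect at that N, naming the effect-size convention and the correlation used. Add a sensitivity range for smaller N, labelled as assumed.
2. **Section 9.3.** Remove the all-10-sessions condition, so that randomised participants with outcome data are analysed in their assigned arm. Keep the full-dose set as a sensitivity analysis.
3. **Section 5.5.** Describe 36 as the number expected to be retained, and state a separate allowance for unusable or missing primary data. Change 2 alone does not make 36 the analysed number, because the usable-data condition and case-wise deletion remain. Participants who discontinue the intervention may also still lack later data, since 7.1 largely ends their assessments.

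The cost is wording and recalculation, with no added participants. The stated N and power become slightly less favourable.

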6 STUDY INTERVENTION(S) OR EXPERIMENTAL MANIPULATION(S)

6.1 STUDY INTERVENTION(S) OR EXPERIMENTAL MANIPULATION(S) ADMINISTRATION

6.1.1 STUDY INTERVENTION OR EXPERIMENTAL MANIPULATION DESCRIPTION

Experimental Manipulation – IBMT (Arm 1): IBMT emphasizes the cooperation between body and mind in facilitating and achieving a meditative state ecologically.^{1-7,18-22} Each IBMT session is facilitated by an experienced and certified coach who has demonstrated the ability to attain the appropriate state of body and mind, and to lead the group to achieve a similar state. The coach creates a harmonious and relaxed atmosphere, observes facial and body cues to identify those who are struggling with the method, and gives proper feedback for effective practice. IBMT coach helps subjects attain desired state by first providing a brief period to induce a cognitive or emotional state that will facilitate

the training. Then, coach helps subjects find an appropriate and balanced body posture and follow instructions to achieve deeper levels of relaxed body (physiology of relaxation) and experience a restful feeling and mental quiet (psychology of relaxation) mindfully.

When the mind wanders, the coach helps subjects accept and be open to experiences without judgment, and further guides subjects to use a favorite mental image as a tool to return to the present moment gently. At last, the coach facilitates a brief group discussion to ensure subjects having positive experiences consistent with the intent of IBMT. The method stresses no effort to control thoughts, but instead emphasizes a state of restful alertness that allows a high degree of awareness of the body, mind, and environment.^{1-7,18-22}

Control Intervention – Health Education (Arm 2): For HE, each session includes pre-, post- and practice sessions, similar to IBMT procedure and is facilitated by a trained coach. However, HE involves teaching participants different health promotion skills, behavior, attitude and strategies, which are guided by the certified coach. Participants have an active group experience that is not mindfulness-related. Therefore, HE induces a comparable but different experience and could serve as an ideal active control. Moreover, other groups have been using HE as active control in RCTs involving mindfulness intervention as an active control condition.^{2,7,64,65}

6.1.2 ADMINISTRATION AND/OR DOSING

Both arms of interventions will be administered as a group by trained interventionists. Both interventions will have 10 consecutive group sessions, and the completion of all 10 sessions is considered to be having a “full-dose” intervention. Participants in the same arm/group will interact with a shared interventionist.

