9.2 SAMPLE SIZE DETERMINATION

Our series of RCTs suggest that IBMT showed significant effects in relatively small sample size ¹⁻⁴⁴. For example, a recent RCT in healthy older adults showed significant effects on quality of life (N=25) and in resting state functional connectivity and structural changes in the ACC/mPFC-Striatum networks following IBMT (N=13) ⁴; In adults, we detected significant fMRI signal changes in the ACC/mPFC (Cohen's $d = .90$) after 10-session IBMT ^{9,11}. We used GPower 3.1 software to determine the smallest detectable effect for a treatment X time interaction term given various sample sizes and a power of 0.80, assuming varying correlations between repeated measures, which ranged from .30 -.60 on behavioral and .50 -.80 on fMRI measures in our prior studies ¹⁻⁴⁴. Considering these factors, our target N of 40 after attrition will allow us to detect small-medium-sized effects on continuous outcomes. The N of 40 will provide a reasonable sample to determine the effect size of IBMT without utilizing an unreasonable amount of resources in this pilot. Specifically, 40 subjects will give us adequate statistical power (80%) to detect a medium effect size [$f = 0.3$ for ANOVA and $h = 0.6$ for proportion difference] with alpha=0.05 for analysis proposed. This effect size is conservatively estimated based on our previous studies ^{5,8-12}. The Chi-square test would be less statistically powerful; however, as the nature of this project is exploratory, we are interested in determining the potential effect size of intervention and in developing our intervention protocol in older adults before testing it in a larger sample size.

Given the 1-year project with pre, post-intervention and follow-up and power considerations, the N of 40 we choose is also in line with our intervention cycles and capacities.

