9.4.2 ANALYSIS OF THE PRIMARY ENDPOINT(S)

The primary endpoints are behavioral and cognitive assessments and are all repeated measures assessed at baseline, post-intervention, and 3-month follow-up. For cognitive assessment of N-Back working memory, percentage of correct trials will be calculated for each trial for all endpoints. For behavioral assessment of emotion regulation, mindfulness, and SCD, these self-report questionnaires will be calculated based on established scoring guides by summing all items within a given questionnaire for all endpoints. Next, the effects of intervention (IBMT vs. HE) on each of these primary endpoints will be examined using repeated-measures ANOVA with time x group interaction effect. Variance and covariance across repeated measures will be calculated as part of the ANOVA. Age and sex will be included as covariates to control for potential confounding effects of age and sex on behavioral and cognitive assessments. Results will be presented as F values for the interaction effect, along with p values to indicate statistical significance. Normality and homogeneity of variance assumptions will be checked using SPSS built-in tools for ANOVA. Because there are 4 primary endpoints, multiple comparison corrections will be conducted using FDR correction. Missing data will be handled with case-wise deletion.

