9.4.3 ANALYSIS OF THE SECONDARY ENDPOINT(S)

The secondary endpoints are brain assessments and are all repeated measures assessed at baseline, post-intervention, and 3-month follow-up. For brain assessment of white matter, white matter integrity metrics will be calculated for all endpoints based on standardized processing pipelines of diffusion-based white matter data using FSL (<http://www.fmrib.ox.ac.uk/fsl>). For brain assessment of grey matter, cortical thickness and volume metrics will be calculated for all endpoints based on standardized processing pipelines of structural MRI data using SPM12 (<http://www.fil.ion.ucl.ac.uk/spm>). For brain assessment of functional connectivity, pair-wise correlations of fMRI timeseries will be calculated for regions of interest and for all endpoints based on standardized processing pipelines of fMRI data using REST software (www.restfmri.net). After these data preprocessing and calculation, numerical values will be generated for all secondary endpoints (white matter, grey matter, and functional connectivity). Next, the effects of intervention (IBMT vs. HE) on each of these secondary endpoints will be examined using repeated-measures ANOVA with time x group interaction effect. Variance and covariance across repeated measures will be calculated as part of the ANOVA. Age and sex will be included as covariates to control for potential confounding effects of age and sex on brain function and structure. Results will be presented as F values for the interaction effect, along with p values to indicate statistical significance. Normality and homogeneity of variance assumptions will be checked using SPSS built-in tools for ANOVA. Because there are 3 secondary endpoints, multiple comparison corrections will be conducted using FDR correction. Missing data will be handled with case-wise deletion.

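### Both arms are delivered in groups with a shared coach, but the outcome tests treat participants as independent; if outcomes within a session group are correlated, the time x arm p-values are too small

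*Combined protocol and SAP*

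**What the plan says.** Section 6.1.2 states that "Both arms of interventions will be administered as a group by trained interventionists", that "Both interventions will have 10 consecutive group sessions", and that "Participants in the same arm/group will interact with a shared interventionist". Section 6.1.1 describes the IBMT coach as someone able "to lead the group to achieve a similar state"; a short group discussion closes each IBMT session. The control is also described there as an active group experience.

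For the primary endpoints, 9.4.2 says the effects "will be examined using repeated-measures ANOVA with time x group interaction effect". Group here means treatment arm (IBMT vs. HE). On adjustment: "Age and sex will be included as covariates to control for potential confounding effects of age and sex on behavioral and cognitive assessments". The only covariance mentioned is that between one participant's repeated measures. Section 9.4.3 repeats the approach: "the effects of intervention (IBMT vs. HE) on each of these secondary endpoints will be examined using repeated-measures ANOVA". Results are F and p values, with FDR correction over four primary and three secondary endpoints; 9.4.1 adds Cohen's d.

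Section 9.2 claims 80% power at N = 40 for f = 0.3 and alpha 0.05, and remarks that "the N of 40 we choose is also in line with our intervention cycles and capacities". No section gives an ICC, a design effect, the number or size of session groups, or the number of coaches.

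**The concern.** People who share a coach, a room and ten sessions can come to resemble one another in outcome. In the IBMT arm that resemblance is close to a stated aim of the coaching. An ANOVA that handles correlation only within a person counts each participant as an independent piece of information about the arm difference. Where session groups share variation, the standard error of the arm contrast is understated, and a session-group effect can pass for a treatment effect.

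At stake are the p-values that 9.4.2 and 9.4.3 use to declare significance, the FDR step that takes them as input, and the uncertainty attached to the effect size that 9.2 wants to carry into a larger trial.

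**Working it through.** **Inputs from the documents.** N = 40 (9.2); 36 expected completers (5.5); three assessments; alpha 0.05; f = 0.3; correlation between repeated behavioral measures 0.30-0.60 (9.2). Allocation balances total numbers (4.1), so I take 20 per arm, or 18 among completers.

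**Assumptions, because the documents are silent.** ICC of the change scores 0.01, 0.05 or 0.10; one group of 20, two of 10, or four of 5 per arm.

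**The plan's own power figure first.** For the time x arm interaction with three assessments, the noncentrality is f² x N x 3 / (1 - rho), with 2 and 76 degrees of freedom. At rho = 0.30 it is 0.09 x 40 x 3 / 0.70 = 15.4, giving power 94.1%; at rho = 0.50 and 0.60, power is 98.8% and 99.7%. These figures assume sphericity. The stated 80% is therefore met as a minimum rather than reproduced, and it contains no allowance for clustering.

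**Effect of clustering on the test.** With session groups of size m:

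- Design effect: DEFF = 1 + (m - 1) x ICC.
- Effective N = 40 / DEFF.
- True standard error / assumed standard error = sqrt(DEFF).
- Actual two-sided type I error = 2 x (1 - Phi(1.96 / sqrt(DEFF))).

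Example: m = 20 and ICC 0.05 give DEFF = 1 + 19 x 0.05 = 1.95; 1.96 / 1.396 = 1.404; type I error 16.0%.

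| Groups per arm | ICC | DEFF | Effective N | SE ratio | Type I, formula | Type I, simulated |
|---|---|---|---|---|---|---|
| One of 20 | 0.01 | 1.19 | 33.6 | 1.09 | 7.2% | 7.3% |
| One of 20 | 0.05 | 1.95 | 20.5 | 1.40 | 16.0% | 16.1% |
| One of 20 | 0.10 | 2.90 | 13.8 | 1.70 | 25.0% | 26.9% |
| Two of 10 | 0.01 | 1.09 | 36.7 | 1.04 | 6.0% | 5.9% |
| Two of 10 | 0.05 | 1.45 | 27.6 | 1.20 | 10.4% | 10.3% |
| Two of 10 | 0.10 | 1.90 | 21.1 | 1.38 | 15.5% | 16.2% |
| Four of 5 | 0.01 | 1.04 | 38.5 | 1.02 | 5.5% | 5.5% |
| Four of 5 | 0.05 | 1.20 | 33.3 | 1.10 | 7.4% | 7.3% |
| Four of 5 | 0.10 | 1.40 | 28.6 | 1.18 | 9.8% | 9.9% |

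The simulated values for one and two groups come from the time x arm ANOVA under the null (20,000 runs, group effect present at post-intervention and follow-up). Those for four groups come from a two-arm t-test on change scores (40,000 runs). At ICC = 0 the simulated ANOVA error is about 5%.

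With one group of 18 completers per arm, the formula gives 7.0%, 15.0% and 23.3%; the simulated ANOVA gives 6.7%, 15.2% and 25.2%.

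**Effect on power** (f = 0.3, rho = 0.30, effective N in place of 40), for ICC 0.01 / 0.05 / 0.10:

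- Two groups of 10 per arm: 92.0% / 81.7% / 68.8%.
- One group of 20 per arm: 89.3% / 67.4% / 47.6%.

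These are optimistic, because they leave out the further loss of degrees of freedom when the group variance has to be estimated. A test on group means with two groups per arm has 2 degrees of freedom and a critical t of 4.30; with three it has 4 and 2.78; with four, 6 and 2.45. With one group per arm it has none.

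**The case against.** The strongest reply is that the error is conditional. At ICC = 0 there is none, and the size is set by an ICC and a group size that the documents do not supply. One ICC range is also applied to questionnaires, N-Back accuracy and MRI metrics alike. This stands: the omission is certain, its size is not.

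The plan also calls itself a pilot and exploratory, with larger trials to follow, and ignoring clustering does not by itself shift the expected mean difference. This limits the consequence but does not rescue the p-values, which the plan uses to indicate significance and feeds into an FDR correction.

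A reader might infer more than the text supports:

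- **That every test is affected.** The baseline t-tests in 9.4.5 use measurements taken before any session.
- **That planned confidence intervals are too narrow.** None are planned. The point would apply only to intervals later derived from this model or put around Cohen's d.
- **That coaches are nested in arm.** Section 6.1.2 can be read as one coach, or even one group, per arm. But 6.2.1 sets a single list of coach criteria for both arms and does not say whether a coach may deliver both, and 9.2 refers to intervention cycles.
- **That both arms hold the closing group discussion.** It is described only for IBMT.
- **That the stated 80% power fails.** With groups of 10 and ICC 0.05 the effective N is about 28, yet power for f = 0.3 is still about 82% at the lowest stated correlation. It drops below 80% in harsher settings, such as one group of 20 at ICC 0.05 or groups of 10 at ICC 0.10.

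**Conclusion.** The concern holds for the outcome tests in 9.4.2 and 9.4.3, conditional on ICC above 0. The design creates session groups with a shared coach; the specified model and the sample size calculation both ignore them, and nothing elsewhere in the plan corrects this.

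Assuming ICC 0.01-0.10 and 20 per arm, the nominal 5% test has an actual error of about 5.5-10% with four groups of 5 per arm, 6-16% with two groups of 10, and 7-27% with one group of 20. With 18 completers in one group per arm the range is about 7-23% by the formula, and up to 25% in simulation. This is an error in a stated analysis that should be corrected before the p-values are used as evidence of an effect. The documents do not allow a single figure for its size.

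**What to change.** 1. In 6.1.2, state the planned number and size of session groups, the number of coaches per arm, and whether a coach may deliver both arms. Record a session-group and a coach identifier for every participant as the sessions run.
2. In 9.4.2 and 9.4.3, with three or more session groups per arm, analyse the outcomes with a mixed model that includes a random session-group effect and uses Satterthwaite or Kenward-Roger degrees of freedom.
3. With fewer groups, report the arm difference in change from baseline at post-intervention and at 3 months. As a sensitivity analysis, multiply its variance by 1 + (m - 1) x ICC over a stated ICC range (for example 0.01-0.10). Label the unadjusted F and p values descriptive. The ICC is then an assumption; with one group per arm it cannot be estimated from the trial.
4. In 9.2, state that the power figure assumes ICC = 0 and show it over the same ICC range.
5. If there is only one group or one coach per arm, state that group or coach effects cannot be separated from the arm effect.

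The cost is SAP wording and two identifiers. The downside is less favourable p-values and stated power. No extra participants or staff are needed.
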